Appendix F General Guidance for the follow-up of laboratory abnormalities by Sanofi

NEUTROPENIA

[figure not shown]
3. **INFORM** the local monitor
4. **INVESTIGATE** previous treatments particularly long-term, even a long time ago, exposure to toxic agents, e.g., benzene, X-rays, etc.
5. **PERFORM** and collect the following investigations (results):
 - RBC and platelet counts
 - Serology: EBV, (HIV), mumps, measles, rubella
6. **DECISION** for bone marrow aspiration: to be taken in specialized unit
7. **COLLECT/STORE** one sample following handling procedures described in PK sections (**for studies with PK sampling**) and freeze one serum sample (5 mL) on Day 1 (cessation of investigational medicinal product) and Day 5 (for further investigations)
8. **MONITOR** the leukocyte count 3 times per week for at least one week, then twice a month until it returns to normal

Note:

- The procedures described in the above flowchart are to be discussed with the patient only in case the event occurs. If applicable (according to local regulations), an additional consent (e.g., for HIV testing) will only be obtained in the case the event actually occurs.
- For individuals of African descent, the relevant value of concern is <1000/mm³

Neutropenia is to be recorded as AE only if at least one of the criteria listed in Section 10.4.3 is met

THROMBOCYTOPENIA

[figure not shown]

Note:

The procedures above flowchart are to be discussed with the patient only in case described in the the event occurs. If applicable (according to local regulations), an additional consent (e.g., for HIV testing) will only be obtained in the case the event actually occurs.

[figure not shown]
Thrombocytopenia is to be recorded as AE only if at least one of the criteria listed in Section 10.4.3 is met

INCREASE IN ALT

[figure not shown]
NOTE: ALT ≥ 3 ULN (IF BASELINE ALT < ULN) OR ALT ≥ 2 TIMES THE BASELINE VALUE (IF BASELINE ALT ≥ ULN) SHOULD BE NOTIFIED WITHIN 24 HOURS TO THE MONITORING TEAM (SEE SECTIONS 10.4.1.3, 10.4.5, AND 10.4.6). IN ADDITION, IF ALT < 3 ULN MEETS A SERIOUSNESS CRITERION, THE EVENT SHOULD BE NOTIFIED WITHIN 24 HOURS TO THE MONITORING TEAM

ACUTE RENAL FAILURE

Acute renal failure is to be recorded as AE only if at least one of the criteria listed in Section 10.4.3 is met

SUSPICION OF RHABDOMYOLYSIS

Suspicion of rhabdomyolysis is to be recorded as AE only if at least one of the criteria listed in Section 10.4.3 is met

DRI11772 Amended Protocol 2

## LIST OF ABBREVIATIONS AND DEFINITION OF TERMS

6MWT:	6-meter walking test
AE:	adverse event
AESI:	adverse event of special interest
ALP:	alkaline phosphatase
ALT:	alanine aminotransferase
AST:	aspartate aminotransferase
ATC:	anatomic or therapeutic categories
BMI:	body mass index
CI:	confidence interval
CIR:	copy increment from reference
CK:	creatine kinase
CMQ:	Customized MedDRA Query
DLCO:	diffusing capacity of the lung for carbon monoxide
ESR:	erythrocyte sedimentation rate
FEV1:	forced expiratory volume in 1 second
FVC:	forced vital capacity
GGO:	Ground Glass Opacification
hsCRP:	high-sensitivity C-reactive protein
ILD:	Identifiable Causes of Interstitial Lung Disease
IMP:	Investigational Medicinal Product
ITT:	intent-to-treat
IVRS:	interactive voice response system
IWRS:	interactive web response system
PK:	pharmacokinetics
PPI:	proton pump inhibitors
RV:	residual volume
SAE:	serious adverse event
SMQ:	Standardized MedDRA Query
SpO2:	peripheral oxygen saturation
TEAE:	treatment-emergent adverse event
TLC:	total lung capacity
UIP:	usual interstitial pneumonitis
WHO-DD:	World Health Organization Drug Dictionary

# 1 OVERVIEW AND INVESTIGATIONAL PLAN

## 1.1 STUDY DESIGN AND RANDOMIZATION

This is a phase 2, proof-of-concept, multicenter, multinational, randomized, placebo-controlled, double-blind, 3-parallel-arm (placebo qw, SAR156597 200mg qw and SAR156597 200mg q2w alternating with placebo every other week), stratified study design.

After a screening phase of up to 4 weeks, patients will be centrally randomized (using allocation from block randomization schedule with stratifying factors) via IRT in a 1:1:1 ratio to 1 of the 3 treatment groups and treated double-blind for approximately 1 year.

Randomization will be stratified according to background therapy in authorized countries at the moment of randomization (patient with background therapy with either pirfenidone or nintedanib versus patient without background therapy). According to protocol amendment No. 10, it is planned to include a maximum of 66% of patient with background therapy.

Only patients with adjudicated IPF status were allowed to be enrolled in the study.

Approximately 300 patients (100 patients per treatment arm) will be recruited and randomized from 109 initiated sites.

## 1.2 OBJECTIVES

### 1.2.1 Primary objectives

The primary objective of this study is to evaluate, in comparison with placebo, the efficacy of 2 dose regimens of SAR156597 (200 mg qw every week and 200 mg q2w every two weeks alternating with placebo every other week) administered subcutaneously during 52 weeks on lung function of patients with IPF.

### 1.2.2 Secondary objectives

The secondary objectives of this study are:

- To evaluate the efficacy of 2 dose levels/regimens of SAR156597 compared to placebo on IPF disease progression
- To evaluate the safety of 2 dose levels/regimens of SAR156597 compared to placebo in patients with IPF
- To evaluate the pharmacokinetics (through plasma concentrations) of SAR156597 200 mg administered subcutaneously during 52 weeks
- To assess the potential immunogenicity of SAR156597

- To evaluate the effect of SAR156597 on circulating biomarkers
- To explore the effect of SAR156597 on quality of life

### **1.3 DETERMINATION OF SAMPLE SIZE**

Approximately 300 patients will be randomized in this study, 100 per treatment arm. Based on the enrollment in prior studies of this population approximately half of the patients are expected to be older than 65.

The sample size calculations are based on the primary efficacy variable of % predicted FVC change from baseline to week 52, with the following assumptions:

- A common standard deviation of 12% is assumed based on the data from previous trials (26)
- A 5% mean difference between each dose and placebo in change from baseline in % predicted FVC
- A 2-sided 5% significance level with 80% power

Ninety two (92) patients per treatment arm will yield 80% power to detect a 5 percentage point difference between the treatment groups and placebo. Additional patients will be randomized in each regimen to allow for dropouts; therefore, approximately 100 patients will be randomized into each treatment arm, for a total sample size of approximately 300 patients for the study.

[figure not shown]
As a rank-based method will be used for analysis the actual power may differ from these calculations, however, calculations based on the ASCEND study (28), which used the same analysis method and endpoint confirm that the planned analysis should have at least 80% power. No adjustment is made for multiplicity since a hierarchical testing procedure is proposed.

Calculations were made using nQuery Advisor 7.0.

### **1.4 STUDY PLAN**

The following figure presents the graphical study design:

**Figure 1 - Graphical study design (screening period, double-blind period and follow-up period)**

R\*: randomization  
Sc: subcutaneous  
D: day  
W: week

Approximately 300 patients will be randomized in a ratio 1:1:1 to the following three treatment arms:

- SAR156597 (qw) arm (n = 100): Patients will receive SAR156597 administered subcutaneously in 200 mg doses once every week (qw)
- SAR156597 (q2w) arm (n = 100): Patients will receive SAR156597 administered subcutaneously in 200 mg doses once every 2 weeks (q2w) alternating with placebo subcutaneously once every 2 weeks
- Placebo (qw) arm (n = 100): Patients will receive placebo subcutaneously once every week.

The study population will be stratified at baseline according to a background therapy with pirfenidone or nintedanib (standard of care for IPF in authorized countries).

The study will last up to 68 weeks as follows:

- Up to 4 weeks of screening
- 52 weeks of study treatment (from Day 1 dosing to Week 52 dosing)
- 12 weeks of follow-up

The total duration will be approximately 64 weeks (excluding screening period) per patient.

## 1.5 MODIFICATIONS TO THE STATISTICAL SECTION OF THE PROTOCOL

This section summarizes major changes to the protocol statistical section with emphasis on changes after study start (after the first patient was enrolled). The protocol history table below gives the timing, rationale, and key details of major changes to the protocol statistical section.

The first patient was screened on 01-May-2015.

The first patient was randomized on 27-May-2015.

**Table 1 - Protocol amendment statistical changes**

Amendment Number	Date Approved	Rationale	Description of statistical changes
10	21-Jul-2015	An early analysis of the main efficacy endpoints and safety data will be performed after the last patient completed the End of treatment visit (Visit 9, week 52) to allow an evaluation of the benefit/risk for the treatment of IPF with SAR156597 and take the decision to move to Phase 3 of clinical development and prepare for future phase 3 studies.	Not applicable.
10	21-Jul-2015	In case of major recruitment issues, a futility analysis could be considered in order to make further decisions regarding trial continuation/discontinuation.	No major recruitment issues occurred during the enrollment therefore no interim analysis was performed.
10	21-Jul-2015	Due to the recent approval of pirfenidone (Esbriet®) and nintedanib (Ofev®) and thus the availability on the market in almost all countries participating in the study, the rate of patients with authorized background therapy is likely to be higher than that initially expected at time of study design. In consequence, in order to limit the impact of background therapy on efficacy and safety assessment of SAR156597 for the treatment of IPF, the rate of patients in the background therapy stratum will be capped to a maximum of 66% (i.e., 33% in the without background therapy stratum).	In protocol: stratification factor was already planned for primary analysis but was not described for secondary analyses.  In SAP, description for secondary analyses and specification whether specific parameters will be described by With/Without Background Therapy status will be specified.
NA	NA	Duration of IMP exposure is defined as: last dose date – first dose date + 14 days, however for 200 mg SAR156597 q2w arm, there is an IMP injection every two weeks alternating with placebo the other week.	Duration of IMP exposure will be defined as: last dose date – first dose date + 7 days.
NA	NA	Change in mITT definition due a too low selection of patients (more than 5% of patients were discarded with the protocol definition).	The new definition is all randomized patients who take at least one dose or part of a dose of IMP. Patients will be analyzed using the treatment arm to which they were randomized. This results in considering all mITT patients

Amendment Number	Date Approved	Rationale	Description of statistical changes
			in efficacy analysis provided that the endpoint was measured or could be calculated (e.g. at least 1 baseline and 1 post-baseline values for imputing and calculating a change).
NA	NA	Baseline definition has been revised because the timeslot between a screening and a baseline value is large (up to 4 weeks) and there will not be several assessments at 52 weeks.	Last available value before first IMP administration.
NA	NA	%predicted DLCO analysis is of interest, it was missing in protocol.	Addition of the %predicted DLCO exploratory endpoint analysis.
NA	NA	
Primary efficacy endpoint - change in week 52 missing data (due to death or lung-transplant) imputation approach: the time-to-death or lung transplant approach is more sensitive in ranking patients. For example, a patient who dies early will be more penalized than a patient who dies lately during the study.
 
Primary efficacy endpoint - change in week 52 missing data (due to reasons other death or lung-transplant) imputation approach:
 
 
patients taking treatment at 52 weeks will be imputed using a linear regression run on their treatment arm completers.
 
patients not taking treatment at 52 weeks will be imputed using a linear regression run on the placebo completers.
 
	
Time-to-death or lung transplants will be used instead of allocating the lowest rank for all died and lung transplanted patients.
 
For patients with a week 52 missing data (due to reasons other than death or lung transplant), depending on treatment intake at 52 weeks, a linear regression will be performed on a particular set of completers.

NA	NA	Disease progression endpoint - change in analysis cut-off date: Day 375 will be used instead of superior boundary of week 52 analysis window (Day 406) in order to prevent from non-random censures.	Patients not meeting the definition for disease progression will be considered censored at the time of their week 52 FVC or DLCO assessment provided that it was performed before Day 375. For patients with a missing week 52 assessment, the censoring time will be the time of the last measured FVC or DLCO assessment. For patients with week 52 assessment performed after Day 375, the censoring time will be Day 375.

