11.3 ANALYSIS POPULATIONS

11.3.1 Efficacy populations

11.3.1.1 Modified intent-to-treat population

The primary population for analysis will be the modified ITT (mITT) population: ITT population with an evaluable primary endpoint. This will consist of all patients who receive at least 1 injection of investigational medicinal product, have a valid baseline % predicted FVC measurement, and have at least one post-baseline % predicted FVC measurement.

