### **2.3.1 Efficacy populations**

#### **2.3.1.1 Modified intent-to-treat population**

The modified intent-to-treat (mITT) population is defined as all randomized patients who received at least 1 dose or part of a dose of the IMP. Patients in the mITT population will be analyzed according to the treatment arm to which they are randomized.

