### 2.4.4.1 Analysis of primary efficacy endpoint(s)

The primary efficacy endpoint will be analyzed on the mITT population. In the primary analysis, assessments at week 52 will be used regardless of whether the patient has previously discontinued treatment.

Due to the non-normality of the endpoint distribution, the absolute change from baseline in % predicted FVC at week 52 as defined in [Section 2.1.3.1](#) will be analyzed in the mITT population using a rank ANCOVA model adjusted on the stratification factor (with/without background therapy). This model will use the ranks of absolute change from baseline to week 52 in % predicted FVC as the outcome and the ranks of baseline % predicted FVC as a covariate. In case of ties, the mean of the corresponding ranks will be assigned.

To summarize, the following steps will be performed:

A) On the pool of arms SAR156597 200mg qw and placebo:

1. Imputation of missing data at 52 weeks

a) Week 52 missing values due to reasons other than death or lung transplant

- i. Patients in active arm and taking treatment at 52 weeks: Missing values at 52 weeks will be imputed using a model estimated from the subset of patients in the active arm who completed the 52-week treatment period and with a week 52 value. The imputation model will be based on a Mixed Model with Repeated Measures (MMRM) with fixed categorical effect of stratification factor (with/without Background Therapy) and repeated categorical effect for time point (baseline, week 12, week 24, week 36, week 52). Parameters will be estimated with the Newton-Raphson algorithm, an unstructured covariance matrix will model the within-patient errors, and the denominator degrees of freedom will be estimated using Satterthwaite's approximation. Missing values at 52 weeks will be imputed using the empirical best linear unbiased prediction (EBLUP).

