- ii. Other patients (patients in active arm and not taking treatment at 52 weeks; or patients in placebo arm): Missing values at 52 weeks will be imputed using a model estimated from the subset of patients in the placebo arm who completed the 52-week treatment period and with a week 52 value. The imputation model will be based on a Mixed Model with Repeated Measures (MMRM) with fixed categorical effect of stratification factor (with/without Background Therapy) and repeated categorical effect for time point (baseline, week 12, week 24, week 36, week 52). Parameters will be estimated with the Newton-Raphson algorithm, an unstructured covariance matrix will model the within-patient errors, and the denominator degrees of freedom will be estimated using

- Satterthwaite's approximation. Missing values at 52 weeks will be imputed using the empirical best linear unbiased prediction (EBLUP).
- iii. When running the imputation model, if the predicted absolute change from baseline calculated from the predicted week 52 value is greater than zero (increases above baseline), it will be set to zero.
  - iv. The non-monotone missing patterns with a week 52 value available will not be imputed.
- b) Week 52 missing values due to lung transplant:
    - i. Any % predicted FVC value assessed after a lung transplant will be considered as missing.
    - ii. No imputation of a week 52 value for % predicted FVC. In step 2, patients will be ranked worse than missing data due to reasons other than death or lung transplant.
  - c) Week 52 missing values due to death :
    - i. No imputation of a week 52 value for % predicted FVC. In step 2, patients will be ranked worse than missing data due to lung transplant.
2. Rank ANCOVA
- a) Ranking within each stratum of the stratification factor (with/without Background Therapy)
    - i. Death: Missing data due to death will be ranked based on a time-to-death, with shortest time until death as the worst (lowest) rank (from 1 to  $n_{\text{stratum,death}}$ ).
    - ii. Lung transplant: Missing data due to lung transplant will be ranked based on a time-to-lung transplant, with shortest time until lung transplant as the worst (lowest) rank (from  $n_{\text{stratum,death}}+1$  to  $n_{\text{stratum,death}}+n_{\text{stratum,lungtransplant}}$ ). So, missing data due to lung transplant will be less penalized than deaths.

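### SAP Table 1 and SAP 2.4.4.1 disagree on whether living, untransplanted patients with only a baseline FVC enter the primary analysis

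*SAP*

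**What the plan says.** Protocol 11.3.1.1 defines mITT by three conditions: an injection, a valid baseline % predicted FVC, and that patients "have at least one post-baseline % predicted FVC measurement".

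SAP 1.5, Table 1, changes this because "more than 5% of patients were discarded with the protocol definition". SAP 2.3.1.1 accordingly defines mITT as "all randomized patients who received at least 1 dose or part of a dose of the IMP", with no FVC condition.

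The same Table 1 entry adds a condition, with an example, on who counts: "in efficacy analysis provided that the endpoint was measured or could be calculated (e.g. at least 1 baseline and 1 post-baseline values for imputing".

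SAP 2.4.4.1 analyses the primary endpoint on the mITT. Step A1a imputes Week 52 values that are missing for reasons other than death or transplant. The imputation model has a "repeated categorical effect for time point (baseline, week 12, week 24, week 36, week 52"). No post-baseline value is asked for. For deaths, "Missing data due to death will be ranked based on a time-to-death, with shortest time until death as the worst (lowest) rank"; transplants are ranked in the same way, just above deaths.

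**The concern.** The two places give different answers for one group: treated patients who are alive, not transplanted, and have a valid baseline but no valid later FVC. Section 2.4.4.1 imputes and ranks them. Table 1, if its example is taken as the rule, leaves them out. Two programmers could build different primary analysis sets from the same SAP.

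The group may not be empty. The first scheduled post-baseline FVC is at Week 12 (SAP 2.1.3.1). A spirometry value counts only if it meets the grade and status requirements in SAP 2.1.3. Visits after treatment discontinuation or study withdrawal are to be done where possible (Protocol 10.3.4 and 10.3.5). Leaving before a valid FVC can depend on treatment, so dropping these patients is a post-randomisation exclusion that may differ between arms. Protocol 4.2.1 aims to collect efficacy outcomes on all randomised patients in order to limit this kind of bias. Protocol 10.3.5 leaves it to the SAP to say how patients lost to follow-up for the primary endpoint are handled, and for this group the SAP gives two answers.

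**Working it through.** **Step 1. Compare the rules by type of treated patient.**

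| Treated patient | Protocol mITT | SAP 2.4.4.1 | SAP Table 1, example read as a rule |
|---|---|---|---|
| Valid baseline and a later valid FVC | in | in | in |
| Valid baseline, died before any later FVC | out | in, ranked by time to death | in, ranked |
| Valid baseline, transplanted, no later FVC | out | in, ranked by time to transplant | in, ranked |
| Valid baseline, alive, no transplant, no later valid FVC | out | in, imputed | **out** |
| No valid baseline | out | no baseline rank or change available | out |

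Only the fourth row is in dispute.

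**Step 2. Can Week 52 be predicted from baseline alone?** The imputation model has baseline among its repeated time points and an unstructured covariance. For a patient in stratum s with baseline y0, the prediction is

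ŷ52 = m52(s) + [cov(52,0) / var(0)] × (y0 − m0(s)),

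with means and covariances estimated from the completers. It needs no later value. By that route the Table 1 test of a calculable endpoint is met; only its example points the other way.

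**Step 3. Reproduce the sample size (SAP 1.3).** Inputs are a difference of 5, SD 12, two-sided 5% and 80% power.

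- Normal approximation: n = 2 × [(1.960 + 0.842) × 12 / 5]² = 90.4, so 91 per arm.
- t-test: 91.4, so 92 per arm, as stated. Power at 92 is 80.3%.
- Allowance: 100 − 92 = 8 per arm, or 24 in total.

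**Step 4. Effect on power.** The number excluded is not given, so this is a range, using the t-test with a share d of 100 per arm excluded and the effect unchanged.

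| d | n per arm | Power |
|---|---|---|
| 5% | 95 | 81.5% |
| 8% | 92 | 80.3% |
| 10% | 90 | 79.4% |

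**Step 5. Effect on the estimate.** Assume that a share d of the active arm is dropped, that these patients would have had placebo-like outcomes, and that the difference among those kept is 5 points. The difference with everyone included is 5 × (1 − d) + 0 × d, so the overstatement is 5 × d.

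- d = 2%: 5 × 0.02 = 0.10 points.
- d = 5%: 5 × 0.05 = 0.25 points, which is 0.25 / 12 = 0.02 SD.

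It would be larger if the dropped patients would have done worse than placebo. Keeping all 100 per arm with d = 5% gives a difference of 4.75 points and 79.5% power.

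**The case against.** The best reply is that 2.4.4.1 governs and contains no exclusion. The Table 1 wording is an example in a summary of changes that covers efficacy endpoints generally. Where the SAP wants a post-baseline value it says so: sensitivity analysis 2, disease progression, 6-MWT, SGRQ, EQ-5D-5L and DLCO all carry the condition. Table 1 is loose elsewhere too, since it calls the primary imputation a linear regression where 2.4.4.1 specifies a repeated-measures model. Sensitivity analysis 1 already imputes on the mITT with a reference-based method and states no post-baseline condition, and counts of missing Week 52 data by cause are planned.

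Much of this stands, and it makes the point a conflict to resolve, not a proven exclusion. It does not remove the conflict. Table 1 states the new rule in the SAP's own voice, its example refers to imputing a change, and 2.4.4.1 does not contradict it expressly. The 2.4.4.1 results table refers to patients included in the analysis but has no row for mITT patients left out.

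Three stronger readings are tempting and not supported:

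- **The new mITT is the old one renamed.** It is not. Early deaths and transplants with no later FVC now enter by rank, and the mortality, exacerbation and hospitalisation analyses need no FVC at all.
- **Early dropouts in general are lost.** Patients who stop treatment are to have the end-of-treatment assessments, including FVC (Protocol 10.1 and 10.1.8), and are then asked back for further FVC (Protocol 10.3.4). The Week 12 window opens on Day 2 (SAP Table 6). Only patients with no valid later FVC are affected.
- **The loss exceeds the dropout allowance.** More than 5% of about 300 is more than 15, so at least 16 across three arms, against 24 allowed in total. That figure is also the loss under the protocol definition, with no split by cause or arm, so it does not measure who would still be excluded.

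**Conclusion.** The concern holds as an unresolved conflict over one defined group. If Table 1 is followed, treated, living, untransplanted patients with only a baseline FVC are mITT by definition but absent from the primary comparison, and nothing in the imputation model requires that.

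The likely size is small. The 0.1 to 0.25 point overstatement rests on two assumptions that the documents neither give nor exclude: 2% to 5% of an active arm affected, and placebo-like outcomes in those patients. It is expressed as a mean difference, whereas the primary test is on ranks, so it is only a guide to scale. Power stays at or above 80% until about 8% per arm is excluded. The reason to act is selection after randomisation and a primary analysis set that cannot be reproduced from the text. The documents do not show that any patient has actually been excluded.

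**What to change.** 1. In SAP Table 1, remove the post-baseline condition as it applies to the primary analysis.
2. In SAP 2.4.4.1, state that treated patients who are alive and untransplanted, with a valid baseline and no later valid FVC, have Week 52 imputed by the placebo-based model of step A1a(ii). As written, an active-arm patient of this kind still on treatment at Week 52 would go to step A1a(i), so the sentence should cover that case expressly.
3. Add a row to the 2.4.4.1 results table with the number of such patients by arm and reason.
4. Keep the analysis without them as a sensitivity analysis.

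The cost is wording and one table row, with no new data. It should be settled before the Week 52 data are unblinded. The downside is a few imputed ranks that carry little individual information and, if those patients are placebo-like, a slightly smaller contrast, as in Step 5 of the working.

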9.1.4 Assessment methods and activity parameters

9.1.4.1 Pulmonary Function Tests will include:

- DLCO: carbon monoxide diffusing capacity, corrected for hemoglobin;
- FVC: forced (expiratory) vital capacity;
- FEV1: forced expiratory volume over one second (only done at screening and at baseline)

- TLC: total lung capacity (body plethysmography) (only done at screening and at baseline)
- RV: residual volume (body plethysmography) (only done at screening and at baseline)

DLCO will be measured locally at the investigational site; spirometry test will be done locally but measured by a central laboratory.

Note: Two PFTs will be performed within 4 weeks prior to dosing one at screening and one at baseline. The first PFT will determine whether the patient qualifies for the study and the second will be averaged with the first one to establish a baseline value.

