### **2.1.3 Efficacy endpoints**

Unless otherwise specified, all efficacy parameters values (scheduled or unscheduled) may be used to provide a value for the primary and secondary efficacy endpoints.

For FVC, FEV1 and FEV1/FVC parameters, a value is considered valid if this is an ATSBEST value with a grade “A” or “B” and a status “CLEAN” or “MANUAL”.

All measurements (scheduled or unscheduled) will be assigned to analysis windows defined in [Table 6](#), in order to provide an assessment of the efficacy parameter at each time point planned to be collected as per protocol. For all post-baseline time points, the value used for the analyses at a given time point (e.g at week 52) is the valid value obtained within the corresponding analysis window. If multiple valid values of a variable exist within an analysis window, the nearest from the targeted study day will be selected. In case of ties, the best value will be considered.

The baseline value is the last available and valid measurement obtained before or equal to the date and time of the first double-blind IMP injection. For patients randomized and not treated, the baseline value is defined as the last available and valid value obtained before or equal to the date and time of randomization.

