    - iii. Other: Absolute change from baseline at 52 weeks in % predicted FVC values will be calculated from observed and imputed week 52 % predicted FVC values and then ranked (from  $n_{\text{stratum,death}}+n_{\text{stratum,lungtransplant}} + 1$  to  $n_{\text{stratum}}$ ).
    - iv. Standardization of ranks using the NPLUS1 option of PROC RANK on SAS with the by statement for the stratification factor (with/without Background Therapy).
  - b) Adjustment on baseline % predicted FVC covariate
    - i. The residuals from the linear regression of response ranks on baseline ranks will be calculated within each stratum of the stratification factor (with/without Background Therapy) using the following PROC GLM on SAS:

```
proc GLM data=xx;  
by stratification_factor;  
model chg_Rank=base_Rank;  
output out=residual r=resid;  
run;
```

- c) Test of treatment effect using the CMH2 option of PROC FREQ on SAS and the residuals as scores
  - i. The qw arm will be compared to placebo using a Mantel-Haenszel mean score chi-square test at a two-sided type-I error level of 5%. This test will be stratified on the stratification factor.

B) On the pool of arms SAR156597 200mg q2w and placebo:

Same steps as A except for 2c: the q2w arm will be compared to placebo using a Mantel-Haenszel mean score chi-square test at a two-sided type-I error level of 5% only if the qw arm versus placebo comparison was significant. This test will be stratified on the stratification factor.

Descriptive statistics for values and changes from baseline will be presented by treatment arm and background therapy status for each time point. The mean (SD) % predicted FVC values and the mean (SD) absolute change from baseline in % predicted FVC over time will be graphically represented by treatment arm and by background therapy status without any imputation.

A specific table will describe the following items by treatment arm and background therapy:

- The number (%) of patients with an observed week 52 value for % predicted FVC
  - The mean (SD) and median (Q1:Q3) of baseline and week 52 values of % predicted FVC for those patients
  - The mean (SD) and median (Q1:Q3) of absolute change from baseline at 52 weeks in % predicted FVC for those patients
- The number (%) of patients having a missing data due to death at week 52,
- The number (%) of patients having a missing data due to lung transplant at week 52,

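### The SAP adjusts the primary FVC test on the last pre-dose value alone, giving up a modest amount of precision that the screening FVC could return; no bias is involved

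*SAP*

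**What the plan says.** Protocol 9.1.4.1 states that "Two PFTs will be performed within 4 weeks prior to dosing one at screening and one at baseline". The first of these has a second use: "The first PFT will determine whether the patient qualifies for the study". For the baseline, "the second will be averaged with the first one to establish a baseline value".

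SAP Table 1 (section 1.5) replaces the average with "Last available value before first IMP administration". It gives two reasons: screening and baseline can be up to 4 weeks apart, and "there will not be several assessments at 52 weeks". The amendment number and approval date for this row are both NA. SAP 2.1.3 repeats the rule for efficacy: "The baseline value is the last available and valid measurement obtained before or equal to the date and time" of the first injection. A screening FVC therefore serves as baseline only when no later valid pre-dose value exists.

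In SAP 2.4.4.1, step 2b, the covariate adjustment within each stratum is "model chg_Rank=base_Rank", with one baseline term. The two sensitivity MMRMs in 2.4.4.1.1 also carry a single baseline covariate. Neither uses the screening value or the average.

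**The concern.** A single spirometry reading contains test-retest error. That error enters the change score in full, and regressing on the same reading removes only part of it. A second reading, taken before randomization and already scheduled for every patient, carries further information about the patient's true starting level.

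The SAP's two reasons are arguments against averaging. The single Week 52 test does not make a second pre-treatment reading less informative. The 4-week gap lowers the weight the screening value deserves, but does not reduce it to zero, and a regression can estimate that weight. So the stated reasons do not explain why the screening value is also absent from the covariate adjustment.

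What is at stake is precision on the primary comparison, in a trial sized for 80% power at 92 evaluable patients per arm.

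**Working it through.** **Inputs from the documents** (protocol 11.1, SAP 1.3): SD of change 12, difference 5, two-sided 5%, 92 per arm for 80% power, about 100 per arm randomized.

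**Inputs assumed**, because the documents give none of them: within-patient test-retest SD e = 2 to 5 points; between-patient SD T = 15 (14 and 16 give nearly the same results); SD of true drift between the two pre-dose tests g = 0, then 2.

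**The plan's own figure.** The standard error is 12 × √(2/92) = 1.769, and 5/1.769 = 2.826. Normal-theory power is Φ(2.826 − 1.960) = 80.7%. The noncentral t gives 79.8% at 91 and 80.3% at 92, so 92 per arm reproduces.

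**Linear model.** Let the change variance be 144 = VarD + 2e², where VarD is the variance of true change.

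- Residual variance with one baseline reading: R1 = VarD + e² + S1, with S1 = T²e²/(T² + e²).
- With both readings as covariates: R2 = VarD + e² + S2, with S2 = 1/(1/T² + 1/e² + 1/(e² + g²)).
- With g = 0, R2 is also the value for the averaged baseline.

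Worked case, e = 3 and g = 0: VarD = 144 − 18 = 126; S1 = 225 × 9/234 = 8.65; S2 = 4.41. Then R1 = 143.65 and R2 = 139.41, a cut of 4.24/143.65 = 3.0%. The share of the baseline-error term removed is 4.24/8.65 = 49%.

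| e | Variance cut, g = 0 | Share of S1 removed, g = 0 | Patient equivalent at 92 per arm, g = 0 | Variance cut, g = 2 |
|---|---|---|---|---|
| 2 | 1.4% | 50% | 1.3 | 0.9% |
| 3 | 3.0% | 49% | 2.8 | 2.4% |
| 4 | 5.0% | 48% | 4.9 | 4.5% |
| 5 | 7.5% | 47% | 7.5 | 6.9% |

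The patient equivalent is 92 × (R1/R2 − 1). Normal-theory power at 92 per arm, using √R2 as the SD, is 81.9% (e = 3), 82.9% (e = 4) and 84.2% (e = 5), against about 81% with one reading.

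**The SAP's actual test.** The primary test is a stratified rank analysis, so the linear figures are only a guide. The stratified rank procedure was simulated at 92 per arm.

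| e | Gain, screening rank as second covariate | Gain, averaged baseline |
|---|---|---|
| 2 | about 0 points | 0.3 points |
| 3 | 0.4 | 1.1 |
| 4 | 1.3 | 2.0 |
| 5 | 1.9 | 3.3 |

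Simulation error is up to about 0.7 points, so only the pattern should be read from this table. The rank covariate captures only part of the linear-model gain.

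In a separate simulation with an assumed 6% of deaths per arm ranked worst, averaging moved power from 65.9% to 66.0% (e = 2), 66.7% to 68.2% (e = 3) and 67.1% to 70.8% (e = 5).

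**Type I error.** It was 4.6% to 4.8% in simulation for the single reading, the two covariates and the average.

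**The case against.** The case for leaving the SAP alone has real strength.

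- **The change is disclosed and reasoned, and does no harm to validity.** This stands. Table 1 states the change and why it was made. A reader might infer from the NA entries that it was made late or with knowledge of the data. The documents do not say so; they simply do not say when it was decided.
- **The gain rests on unstated figures and may be very small.** This stands. Spirometry is centrally measured and only grade A or B values are accepted, so e could be near or below 2. At e = 1 and g = 2 the linear model has averaging losing 0.3% of variance and the covariate gaining 0.1%.
- **The 4-week gap also weakens the screening value as a covariate.** This stands in part. The g = 2 column shows a smaller gain, but still a gain.
- **Neither document planned two baseline covariates.** True. The proposal is a third option: it keeps the SAP's change score and uses a reading the protocol meant to use. It improves precision; it does not correct an error.
- **Power at 92 overstates the fragility.** Fair. About 100 per arm are randomized, and under the plan's normal assumptions power at 100 is 83.4%, before any effect of deaths or of ranking.

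The screening test's role in eligibility is no objection. It precedes randomization, so adjusting for it does not bias the comparison.

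**Conclusion.** The point holds as a small, optional improvement in precision. The SAP leaves a scheduled pre-randomization measurement of the primary variable out of the primary adjustment, and its stated reasons do not require that. The gain is about 1% to 7.5% of residual variance in a linear model. In the planned rank test it is about 0 to 2 points of power with the second covariate and about 0.3 to 3 points with the average. These figures depend on an assumed test-retest SD of 2 to 5 points with little or no drift between tests.

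Three stronger readings are not supported:

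- Using the second reading does not recover most of the loss from baseline error. It removes just under half when the two readings are equally noisy and there is no drift, and less with drift.
- It is not free of cost, because it needs a missing-value rule and matching edits elsewhere.
- The SAP does not discard the screening value altogether, because that value remains the fallback baseline.

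**What to change.** Before unblinding:

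1. Keep the last valid pre-dose value as baseline for the change score.
2. In SAP 2.4.4.1, step 2b, rank screening % predicted FVC within stratum and add it: `model chg_Rank=base_Rank screen_Rank`.
3. Make the same change in the residual steps of the subgroup analyses (2.4.4.1.2, A and B), so that they still mirror the primary analysis. Add screening % predicted FVC as a covariate in both sensitivity MMRMs.
4. Where no separate valid screening value exists, including when screening is itself the fallback baseline, set the screening covariate equal to baseline.
5. Report the primary test with the protocol's averaged baseline as a sensitivity analysis, using the single valid value when only one exists.
6. State in Table 1 when the baseline change was decided relative to unblinding.

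This needs no extra visit or test. The cost is the rule in item 4, short code edits and one more sensitivity table. The number of patients to whom the rule would apply is not given in the documents and should be reported.
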